Appendix 7. Common Terminology Criteria For Adverse Events (Infusion Reactions)

Adverse Event	Short Name	Grade				
		1	2	3	4	5
Allergic reaction/ Hypersensitivity (including drug fever)	Allergic Reaction	Transient flushing or rash; drug fever $<38^{\circ}\text{C} (<100.4^{\circ}\text{F})$	Rash; flushing; urticaria; dyspnea; drug fever $\geq 38^{\circ}\text{C} (\geq 100.4^{\circ}\text{F})$	Symptomatic bronchospasm, with or without urticaria; parenteral medication(s) indicated; allergy-related edema/angioedema; hypotension	Anaphylaxis	Death
Remark: Urticaria with manifestations of allergic or hypersensitivity reaction is graded as Allergic reaction/hypersensitivity (including drug fever).						
Hypertension	Hypertension	Asymptomatic, transient (<24 hrs) increase by $>20 \text{ mmHg}$ (diastolic) or to $>150/100$ if previously WNL; intervention not	Recurrent or persistent (≥ 24 hrs) or symptomatic increase by $>20 \text{ mmHg}$ (diastolic) or to $>150/100$ if previously WNL; monotherapy may be indicated	Requiring more than one drug or more intensive therapy than previously	Life-threatening consequences (eg, hypertensive crisis)	Death
Hypotension	Hypotension	Changes, intervention not indicated	Brief (<24 hrs) fluid replacement or other therapy; no physiologic consequences	Sustained (≥ 4 hrs) therapy, resolves without persisting physiologic consequences	Shock (eg, acidemia; impairment of vital organ)	Death
Fever (in the absence of neutropenia, where neutropenia is defined as ANC $<1.0 \times 10^9/\text{L}$)	Fever	$38.0 \text{ to } 39.0^{\circ}\text{C} (100.4 \text{ to } 102.2^{\circ}\text{F})$	$>39.0 \text{ to } 40.0 \text{ degrees C}$ ($102.3 \text{ to } 104.0^{\circ}\text{F}$)	$>40.0^{\circ}\text{C} (>104.0^{\circ}\text{F})$ for ≤ 24 hrs	$>40.0^{\circ}\text{C}$ ($>104.0^{\circ}\text{F}$) for >24 hrs	Death
Remark: The temperature measurements listed are oral or tympanic.						
Rigors/chills		Mild	Moderate, narcotics indicated	Severe or prolonged, not responsive to narcotics	--	--
Cytokine release syndrome/acute infusion reaction	Cytokine release	Mild reaction; infusion interruption not indicated; intervention not indicated	Requires therapy or infusion interruption but responds promptly to symptomatic treatment (eg, antihistamines, NSAIDS, narcotics, IV fluids); prophylactic medications indicated for ≤ 24 hrs	Prolonged (ie, not rapidly responsive to symptomatic medication and/or brief interruption of infusion); recurrence of symptoms following initial improvement; hospitalization indicated for other clinical sequelae (eg, renal impairment, pulmonary infiltrates)	Life-threatening; pressor or ventilatory support indicated	Death

Remark: Cytokine release syndromes/acute infusion reactions are different from Allergic/hypersensitive reactions, although some of the manifestations are common to both AEs. An acute infusion reaction may occur with an agent that causes cytokine release (eg, monoclonal antibodies or other biological agents). Signs and symptoms usually develop during or shortly after drug infusion and generally resolve completely within 24 hrs of completion of infusion. Signs/symptoms may include: Allergic reaction/hypersensitivity (including drug fever); Arthralgia (joint pain); Bronchospasm; Cough; Dizziness; Dyspnea (shortness of breath); Fatigue (asthenia, lethargy, malaise); Headache; Hypertension; Hypotension; Myalgia (muscle pain); Nausea; Pruritis/itching; Rash/desquamation; Rigors/chills; Sweating (diaphoresis); Tachycardia; Tumor pain (onset or exacerbation of tumor pain due to treatment); Urticaria (hives, welts, wheals); Vomiting.

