3.2. Sentinel Dosing

In view of the mechanism of action (B cell and cTfh cell depletion), the interval between sentinel subjects and the remainder of the cohort is proposed to mitigate any unanticipated acute safety risks (ie, infusion/injection site reactions). Sentinel dosing will be employed as follows:

- In Part A, for Cohorts A1-A4 (with 4 subjects planned), subjects will be dosed IV at least 24 hours apart. In order to avoid investigator unblinding, the one subject on placebo in these cohorts may be enrolled in any sequence. The sponsor medical monitor will communicate with investigator(s) from each site after dosing of each subject (and prior to dosing of the next subject) in order to determine whether it is safe to proceed with continued dosing within a cohort.

If the sponsor decides to increase the number of subjects in these A1-A4 cohorts, the sentinel dosing will apply only to the first four subjects as described in the paragraph above. After the sponsor medical monitor determines it is safe to proceed, the remaining subjects can be enrolled and dosed simultaneously.

- In Part A, for cohorts A5-A8 (with more than 4 subjects planned), the first two subjects dosed IV will include one PF-06835375 and one placebo subject. If safety and tolerability profile is acceptable in these two subjects, dosing of additional subjects can occur 24 hours after dosing of the first two subjects. These additional subjects within a cohort may be enrolled and dosed simultaneously. The determination to proceed with dosing of additional subjects will be made by the sponsor following communication between sponsor medical monitor and investigator(s) from sites which enrolled sentinel subjects.
- In Part B, for all SC cohorts, sentinel dosing for the first two subjects (as described for Cohort A5-A8 above) will only be employed if a given SC dose level (or higher) was not previously tested in Part A using the IV route of administration. For example, if Cohort A4 (single 1 mg IV dose) has not been tested, sentinel dosing will be used in Cohort B2 (two SC doses of 1 mg). If safety and tolerability profile is acceptable in two subjects after the first of two doses, dosing of additional subjects can occur 24 hours after dosing of the first two subjects.

If in Part B the SC bioavailability is low and the decision is made to change the route of administration to IV, then sentinel dosing in Part B will not be repeated for dose levels already administered in Part A.

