- In Part A, for cohorts A1-A4 (with 4 subjects planned), 4 subjects have completed two weeks post-dose in the study. In Part A, for Cohorts A5-A8 and B1-B5 (with 8 subjects planned), 6 subjects must complete two weeks post-dose in the study.
- The majority of subjects dosed with PF-06835375 in a given cohort have a detectable B cell count (obtained from the CLIA certified central lab; LLOQ = 1 B cell per μ L of blood) for a minimum of 2 consecutive visits at least 2 weeks apart, starting at Week 12. Subjects, who reach detectable B cell counts and withdraw from the study earlier, will be considered as having met this criterion. Subjects who withdraw from the study prior to reaching a detectable B cell count will not be counted in the cohort size (this will be limited to 1 subject per cohort of 4 or 2 subjects per cohort of 8). Investigators will have access only to de-identified B-cell count data to remain blinded.
- The sponsor and majority of investigators with active subjects and/or subjects enrolled in the dose level under review (includes only subjects who received IP) agree to proceed to the next dose level based on the overall safety profile. For the purpose of defining the majority of investigators, only one investigator from each site will be counted.

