3.4.2. Dose Escalation Stopping Rules

Dose escalation stopping rules will be used to determine whether the maximal tolerated dose has been attained. Dose escalation will be stopped if it is determined that the limits of safety and/or tolerability have been reached based on the criteria described in this section. This decision will be made after a discussion takes place between the sponsor study team and the investigator. The sponsor study team may not overrule the investigator's decision to stop dose escalation. If dose escalation is stopped because of any of these criteria, additional cohorts may receive the same or lower doses of the investigational product.

The dose escalation will be terminated based on the following criteria:

- If ≥ 2 subjects within a dose cohort develop *Common Terminology Criteria for Adverse Events* (CTCAE) v4.0 Grade 3 adverse event considered to be serious (ie, SAE) in the same organ system, or if 1 subject develops a CTCAE v4.0 Grade 4 or higher SAE, considered related to study drug, and not clearly related to the underlying disease (ie SLE or RA) process, concomitant medications or supplements.
- Laboratory abnormalities known to be associated with B-cell depleting therapies (neutropenia, thrombocytopenia and anemia) will not be considered for this criterion, instead these laboratory abnormalities will be considered for Individual Stopping Rules ([Section 3.4.3](#)).
- If 50% or more subjects within a dose cohort experience a CTCAE v4.0 Grade 3 or higher infusion reaction as defined by the criteria in [Appendix 7](#).
- If a confirmed or probable case of Progressive Multifocal Leukoencephalopathy is observed, the sponsor will hold dosing for all subjects until the benefit risk assessment of PF-06835375 is re-evaluated by the sponsor (See [Section 7.1.14](#)). If the sponsor concludes the benefit risk assessment is favorable, investigators will be consulted on whether to proceed as described in this section.
- If, at any dose level, the mean exposure for the treatment group reaches or exceeds the exposure stopping limit of C_{av} of 261 $\mu\text{g}/\text{mL}$, OR, based on the observed data, the group mean C_{av} of the next planned dose is projected to exceed the exposure stopping limit (See [Section 1.3](#)). Modified doses may be explored if they are not expected to exceed PK stopping criteria.

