7.1.12. Infusion Site Reactions

Subjects will be continuously monitored for infusion site reactions from the start of drug administration until the end of infusion and then at time points indicated in the [Schedule of Activities](#). Infusion site reactions may be monitored beyond the time points indicated in the [Schedule of Activities](#) based on investigator's assessment.

Infusion reactions may include but are not limited to: rash, flushing, hypotension, tachycardia, throat irritation or discomfort, difficulty swallowing, fever, chills. Any signs or symptoms related to either an infusion or injection site reaction(s) should be treated according to the investigator's standard of care and reported as adverse events. See [Appendix 7](#) for details regarding the grading of adverse events arising from infusion reactions. Infusion reactions will be categorized according to the following definitions:

1. **Acute:** From start of infusion to 2 hours after the infusion. Infusion reaction AEs that occur during this time period be further classified as follows:
 - a. **Serious:** Infusion reactions that meet the criteria of an SAE.
 - b. **Dose interrupted:** Associated with temporary or permanent interruption and/or modification in dose.
 - c. Infusion reaction AEs based on investigator's judgment.
2. **Immediate:** 2 hours after the infusion to 24 hours after initiation of treatment. Infusion reaction AEs that occur during this time period can be further classified as follows:
 - a. **Serious:** Infusion reactions that meet the criteria of an SAE.
 - b. Infusion reaction AEs based on investigator's judgment.
3. **Late (delayed):** 2 days to 14 days after initiation of treatment:
 - a. **Serious:** Infusion reactions that meet the criteria of an SAE.
 - b. Infusion reaction AEs based on investigator's judgment.

Information regarding infusion reactions will be collected on the Adverse Event Record. If the infusion reaction requires a modification to the administration of test article, the information must be recorded on the Test Article Record. All infusion reactions that are considered SAEs should be reported as specified in [Section 8.2.3](#).

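### Appendix 7 lets hypotension treated for 4 to under 24 hours fit both Grade 2 and Grade 3, with no tie-break, at the boundary used by the 50% stopping rule and the SAP severity mapping

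*Protocol*

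**What the plan says.** The hypotension row of Protocol Appendix 7 has two adjacent cells that carry a duration of therapy:

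- Grade 2: "Brief (<24 hrs) fluid replacement or other therapy; no physiologic consequences"
- Grade 3: "Sustained (≥ 4 hrs) therapy, resolves without persisting physiologic consequences"

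The table is operative. One of the escalation stopping criteria in Protocol 3.4.2 refers to this appendix and reads "If 50% or more subjects within a dose cohort experience a CTCAE v4.0 Grade 3 or higher infusion reaction as defined by the criteria". Protocol 7.1.12 sends raters to the same appendix "for details regarding the grading of adverse events arising from infusion reactions", and it names hypotension among the reactions to expect: "Infusion reactions may include but are not limited to: rash, flushing, hypotension, tachycardia".

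SAP 8.3.4 says that infusion-related events were recorded on the CRF by toxicity grade. It maps grades 0 to 2 to mild, 3 to moderate and 4 to severe for the adverse event summaries. Severity of treatment-emergent events is among the primary endpoints in Protocol Section 2.

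**The concern.** Adjacent grades on a severity scale should not share cases. Here they do, at the Grade 2/3 boundary, which is the one the stopping rule uses. Two raters could apply the table correctly to the same event and record different grades. Nothing in Appendix 7 or Protocol 7.1.12 says which grade to take when two cells fit.

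Two uses are exposed. The first is the count of subjects with Grade 3 or higher reactions in a cohort, where planned cohorts of 4 or 8 mean that one grading can decide whether 50% is reached. The second is the severity category in the SAP summaries, where the same event can be mild or moderate.

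**Working it through.** **Inputs.** Duration limits: Appendix 7, hypotension row. Stopping rule and review procedure: Protocol 3.4.2. Cohort sizes: Protocol Table 2 (A1 to A4: 3 active and 1 placebo; A5 to A8 and B1 to B5: 6 active and 2 placebo). Severity mapping: SAP 8.3.4. No sample-size or power figure is at issue.

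**Step 1: overlap.** Let D be hours of therapy. Grade 2 needs D < 24 and Grade 3 needs D ≥ 4. Both hold for 4 ≤ D < 24, a range of 24 − 4 = 20 hours. For an event with no physiologic consequences:

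| D | Cells met |
|---|---|
| 3 h | Grade 2 |
| 6 h | Grade 2 and Grade 3 |
| 20 h | Grade 2 and Grade 3 |
| 30 h | Grade 3 |

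**Step 2: the consequences condition.** Grade 2 requires no consequences; Grade 3 requires only that none persist. An event of 4 to under 24 hours with transient consequences that resolve therefore fits Grade 3 only. The double grading is confined to events with none.

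**Step 3: other rows.** The allergic-reaction row lists hypotension under Grade 3. The cytokine-release row names hypotension as a possible sign, and its Grade 3 covers reactions that do not respond rapidly. A subject who is Grade 3 under either row already counts towards the rule, whichever hypotension cell is read.

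**Step 4: comparison within the table.** Hypertension divides at under 24 versus 24 hours or more, and fever at up to 24 versus over 24 hours. Hypotension is the only row whose adjacent duration limits cross.

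**Step 5: when one grading is pivotal.** The smallest count reaching 50% of n subjects is n/2 rounded up: 2 of 4 and 4 of 8. If only active subjects were counted, it would be 2 of 3 and 3 of 6.

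- Cohort of 8, three undisputed Grade 3 reactions and one disputed case: 3/8 = 37.5% (not met) if Grade 2; 4/8 = 50% (met) if Grade 3.
- Cohort of 4, one undisputed and one disputed: 1/4 = 25% or 2/4 = 50%.

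**Step 6: illustration under assumed rates, which are not in the documents.** Take a cohort of 8 with reactions in the 6 active subjects only and 4 reactions needed. Let p be the undisputed Grade 3 or higher rate and q the disputed hypotension rate. P(rule met) is P(X ≥ 4), where X is binomial(6, p) if every disputed case is Grade 2 and binomial(6, p + q) if every one is Grade 3.

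| p | All read as Grade 2 | All read as Grade 3, q = 0.10 | q = 0.30 |
|---|---|---|---|
| 0.05 | 0.0001 | 0.0059 | 0.1174 |
| 0.10 | 0.0013 | 0.0170 | 0.1792 |
| 0.20 | 0.0170 | 0.0705 | 0.3438 |

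These show the direction and possible reach of the ambiguity before the review procedure in Step 7. They are not estimates for this trial.

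**Step 7: the review procedure.** Under Protocol 3.4.2 a dose review team decides whether a criterion is met. If it cannot agree unanimously, dosing at that level ends and escalation does not proceed. A disagreement over Grade 2 versus Grade 3 in a pivotal case therefore already leads to stopping. The outcome depends on the overlap only where all members take the Grade 2 reading.

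**Step 8: reporting.** Under SAP 8.3.4 the two readings place the same event in mild or in moderate, one category apart.

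**The case against.** The strongest objection is that the finding rests on one printed figure. Every other hour limit in Appendix 7 is 24, and the table as supplied shows some lost text elsewhere: the hypertension Grade 1 cell breaks off. The 4 could be a digit dropped in reading the PDF. That is a fair reason to look at the source page first, and if that page prints limits that do not cross, the point falls away. It is not shown, however: the cell is otherwise intact, and the limit of 24 hours or more in the hypertension row was read correctly.

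The second objection is that the review procedure in 3.4.2 protects against the error. This largely stands. A reader might infer that the rule's outcome simply follows from the cell a rater happens to read. The documents do not support that, because lack of unanimity means stopping. The default does not help when nobody at the meeting raises the second reading.

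Third, 20 of 24 hours (83%) might be read as the share of Grade 2 hypotension events affected. It is a share of clock time; no incidence or distribution of treatment duration is given.

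Fourth, the rule is worded for infusion reactions, while Part B was planned as SC, with injection-site reactions graded under Appendix 8. SAP Table 1 records A7, A8 and X6 as not used. Most of the prospective effect on escalation therefore appears to be past. This stands.

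Fifth, the SAP does not plan dedicated tables of reactions by grade. It plans listings and a mapping into the standard severity summaries. This also stands, and limits the reporting effect to a move between mild and moderate.

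**Conclusion.** As supplied, the two hypotension cells contradict each other for events treated for 4 to under 24 hours with no physiologic consequences, where no other row already gives Grade 3. The table offers no tie-break. The defect is worth correcting because it lies on the threshold used by a safety stopping rule and by the SAP severity mapping.

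Its effect is limited. Stopping is affected only by pivotal cases that the whole dose review team reads as Grade 2. With the SAP's account of which cohorts were used, the live consequences are the mild or moderate label in the adverse event summaries and any later statement on whether a cohort met the 50% criterion. The frequency cannot be derived, and nothing in the documents shows that such an event occurred or was misgraded.

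The conclusion assumes that the source page prints the limits as supplied, and that the CRF toxicity grades were assigned with Appendix 7, as Protocol 7.1.12 directs.

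**What to change.** 1. Check the hypotension row on the source page of Appendix 7. If the limits there do not cross, no further action is needed.
2. If they are as supplied, reconcile the Grade 2 and Grade 3 cells so that each duration of therapy falls in exactly one grade. Which limit applies is for the sponsor to decide; none is proposed here.
3. Before the mapping in SAP 8.3.4 is applied, check the grade of any recorded infusion-related hypotension with 4 to under 24 hours of therapy, and document the outcome.

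The cost is one cell edit and a small data check. Protocol 5.6 asks for start and stop dates of concomitant treatments and does not mention times, so hours of therapy may have to come from site source records.

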Appendix 8. Antigen Local Reactivity Due to IP or Vaccine Challenges

All local reactions at the site of IP injection or antigen injections **CCI** will be recorded as AEs. Antigen injection sites will be monitored for pain, tenderness, erythema and swelling using the intensity grading scheme presented below

Injection Site Reaction Grading Scheme

Reaction	Intensity Grading				Potentially Life-threatening
	Mild	Moderate	Severe		
Pain	Does not interfere with activity	Repeated use of non-narcotic pain reliever >24 hours or interferes with activity	Any use of narcotic pain reliever or prevents daily activity		Emergency room visit or hospitalization
Tenderness	Mild discomfort to touch	Discomfort with movement	Significant discomfort at rest		Emergency room visit or hospitalization
Erythema/redness	2.5 to 5 cm	5.1 to 10 cm	>10 cm		Necrosis or exfoliative dermatitis
Induration/swelling	2.5 to 5 cm and does not interfere with activity	5.1 to 10 cm or interferes with activity	>10 cm or prevents daily activity		Necrosis

CCI

Appendix 10. Patient's Global Assessment (PtGA) of Arthritis

CONSIDERING ALL THE WAYS YOUR ARTHRITIS AFFECTS YOU, HOW ARE YOU FEELING TODAY?

(PLEASE MAKE AN X MARK ON THE LINE BELOW.)

Very _____ Well _____ Very _____ Poorly

[Note: Scale will be 100 mm in length]

CCI

1. AMENDMENTS FROM PREVIOUS VERSION(S)

- Section 2.1
 - Added a description of the cohorts actually used, and the actual doses to the description of planned cohorts and doses.
- Section 2.3
 - Added mapping of the analyses required for evaluation of exploratory objectives to SAP and bSAP.
- Section 6.3
 - Separated table for PK parameters into the separate tables for single dose and multiple doses phases of the trial.
- Sections 6.4, 6.5
 - Updated mapping of endpoints to SAP and bSAP analyses.
- Section 6.6
 - Added plots for time to ADA/NAb detection, spaghetti plots of PK, **CCI** [REDACTED], and PK concentration and parameter summary by ADA/NAb status.
- Section 8.2.2
 - Separated table for PK parameters into the separate tables for single dose and multiple doses phases of the trial.
- Section 8.2.3
 - Added description of pharmacodynamic analyses.
 - Removed semi-log scale plots for CFB outcomes; removed subject level plots for **CCI** [REDACTED].
- Section 8.3.4
 - Described additional analyses: mapping of toxicity to severity and search for adverse events that may be caused by the cytokine release syndrome.

2. INTRODUCTION

PF-06835375 is a humanized, afucosyl immunoglobulin (Ig) G1 antibody against C-X-C chemokine receptor type 5 (CXCR5), a surface receptor that is expressed on B cells, *bona fide* follicular T helper (Tfh) cells, and circulating follicular T helper-like (cTfh) cells.

The goal of this first in human (FIH) study is to evaluate the safety, tolerability, pharmacokinetics (PK), and pharmacodynamics (PD) of PF-06835375. In particular, PD characterization will include assessment of magnitude and duration of CXCR5-positive cell depletion and recovery. Inhibition of the humoral immune responses via PF-06835375-mediated depletion of CXCR5-positive cells offers the potential for clinical evaluation in a population of seropositive autoimmune participants. Consequently, a mixed population of seropositive SLE or RA participants will be enrolled into this study.

2.1. Study Design

This is a Phase 1, randomized, multi-center, double-blind, sponsor open, placebo-controlled, single and multiple dose-escalation study to evaluate the safety, tolerability, pharmacokinetics, and pharmacodynamics of PF-06835375 in participants with seropositive SLE or RA. Both IV and SC routes of administration will be tested.

This study will include two parts: Part A, consisting of approximately eight single ascending dose (SAD) cohorts, and Part B, consisting of approximately 6 multiple ascending dose (MAD) cohorts. Cohorts in Part A will be initiated sequentially. Participants in Part B will receive two doses of investigational product (first dose on Day 1 and second dose on Day 29), and will be enrolled concurrently with Part A following the completion of the initial cohorts in Part A. Participants who are randomized in Part A will not be eligible to participate in Part B of this study.

The study includes a Screening visit to assess eligibility and subsequent visits for a minimum of 16 weeks. Participants who meet the end of study criteria will have one follow-up phone call visit which will represent the end of study visit (unless additional follow up is needed for safety reasons or unresolved AEs attributable to immunogenicity). Participants, who do not meet the criteria to leave the study at Week 16, will continue with clinic visits every four weeks until they meet these criteria. Overall, participants are expected to stay in the study approximately 6-12 months (including screening). Participants who withdraw from the study may be replaced at the discretion of the sponsor. A replacement subject will receive the same treatment as the withdrawn subject.

Both SLE and RA participants will be enrolled into this study. Minimum disease activity (ie, SLEDAI-2K or DAS28 cutoffs) is not required for entry as inclusion criteria. All subjects in both Part A and B will be followed for a minimum of 16 weeks prior to being able to qualify for study completion based on the cellular recovery.

It is at the sponsor's discretion to dose escalate, to repeat the same dose, or to test a lower dose based on emerging data.

The PD effects of PF-06835375 on the immune system will be evaluated using multiple biomarkers, including extensive longitudinal flow cytometry assessment pre- and post-administration of IP (investigational product). In addition, the functional effects of PF-06835375 will be assessed with two vaccine challenges CCI

CCI

Throughout the study, B cell counts obtained from a CLIA (Clinical Laboratory Improvement Amendments) certified central lab will be used for clinical decision making (inclusion/exclusion criteria, dose escalation, initiation of Part B and for the end of study criteria).

Figure 1 (below) shows the study schematic and [Table 1](#) shows the planned cohorts and actual dosing regimens Cohorts A7, A8, X6 were not used, the doses in both cohorts A6 and B4 were both reduced from 10 mg to 6 mg and the dose in cohort B5 was reduced from 30 mg to 10 mg.

Figure 1. Study Schematic

[figure not shown]

Table 1. Planned Cohorts

Cohort Name	Administration Route	Proposed Human Dose ^a (mg)	Actual dose (mg)	Expected Number of Participants Per Cohort ^c
Part A (SAD)				
A1	IV	0.03	0.03	3a, 1p
A2	IV	0.1	0.1	3a, 1p
A3	IV	0.3	0.3	3a, 1p
A4	IV	1	1	3a, 1p
A5	IV	3	3	6a, 2p
A6	IV	10	6	6a, 2p
A7	IV	30	Not used	6a, 2p
A8	IV	100	Not used	6a, 2p
Part B (MAD)				
B1	SC ^b	0.3	0.3	6a, 2p
B2	SC ^b	1	1	6a, 2p
B3	SC ^b	3	3	6a, 2p
B4	SC ^b	10	6	6a, 2p
B5	SC ^b	30	10 mg	6a, 2p
X6 ^d	SC ^b	up to 30	Not used	Up to 24 total (16a, 8p)

Abbreviations: a = active, p = placebo; IV = Intravenous; SC = subcutaneous

a. Doses may be changed based on available emerging safety, tolerability, PK and PD.

b. Route of administration may be changed based on available emerging safety, tolerability, PK and PD.

c. Sponsor may elect to add more subjects into the planned cohorts for any reason, including but not limited to eg, subject withdrawal, higher than expected PD effect, etc. The study will enroll up to a total of approximately 112 participants.

d. Optional cohort called "X".

